6.3 Statistical analyses

This section describes the final study analysis, unblinded as to treatment arm assignment. All data from enrolled participants will be analyzed regardless of how many vaccinations they received. In the rare instance that a participant receives the wrong treatment at a specific vaccination time, the Statistical Analysis Plan (SAP) will address how to analyze the participant's safety and immunogenicity data. Analyses are modified intent-to-treat in that individuals who are randomized but not enrolled do not contribute data and hence are excluded. Because of blinding and the brief length of time between randomization and enrollment—typically no more than 4 working days—very few such individuals are expected.

Analyses for primary endpoints will be performed using SAS and R. All other descriptive and inferential statistical analyses will be performed using SAS, StatXact, or R statistical software.

For the primary and secondary immunogenicity analysis comparisons, the following groups may be pooled: groups 1 and 4, groups 2 and 5, groups 3 and 6. Unpooled group comparisons will also be considered.

No formal multiple comparison adjustments will be employed for multiple safety endpoints, multiple primary immunogenicity endpoints, or secondary endpoints. However, multiplicity adjustments will be made for certain immunogenicity assays, as discussed below, when the assay endpoint is viewed as a collection of hypotheses (eg, testing multiple peptide pools to determine a positive response).

6.3.1 Analysis variables

The analysis variables consist of baseline participant characteristics, safety, and immunogenicity for primary- and secondary-objective analyses.

6.3.2 Baseline comparability

Treatment arms will be compared for baseline participant characteristics using descriptive statistics.

6.3.3 Safety/tolerability Analyses

Since enrollment is concurrent with receiving the first vaccination, all participants will have received at least 1 vaccination and therefore will provide some safety data.

6.3.3.1 Reactogenicity

The number and percentage of participants experiencing each type of reactogenicity sign or symptom will be tabulated by severity and treatment arm and the percentages displayed graphically by arm. For a given sign or symptom, each participant's reactogenicity will be counted once under the maximum severity for all injection visits. In addition, to the individual types of events, the maximum severity of local pain or tenderness, induration or erythema, and of systemic symptoms will be calculated. Kruskal-Wallis tests will be used to test for differences in severity between arms.

6.3.3.2 Adverse events (AEs) and serious adverse events (SAEs)

Adverse events (AEs) will be summarized using Medical Dictionary for Regulatory Activities (MedDRA) System Organ Class and preferred terms. Tables will show by treatment arm the number and percentage of participants experiencing an AE within a System Organ Class or within preferred term category by severity or by relationship to study product. For the calculations in these tables, a participant with multiple AEs within a category will be counted once under the maximum severity or the strongest recorded causal relationship to study product. Formal statistical testing comparing arms is not planned since interpretation of the magnitude of differences must rely heavily upon clinical judgment.

A listing of SAEs reported to the DAIDS Regulatory Support Center (RSC) Safety Office will provide details of the events including severity, relationship to study product, time between onset and last vaccination, and number of vaccinations received.

6.3.3.3 Local laboratory values

Box plots of local laboratory values will be generated for baseline values and for values measured during the course of the study by treatment arm and visit. Each box plot will show the first quartile, the median, and the third quartile. Outliers (values outside the box plot) will also be plotted. If appropriate, horizontal lines representing boundaries for abnormal values will be plotted.

For each local laboratory measure, summary statistics will be presented by treatment arm and timepoint, as well as changes from baseline for postenrollment values. In addition, the number (percentage) of participants with local laboratory values recorded as meeting Grade 1 AE criteria or above as specified in the

Division of AIDS (DAIDS) Table for Grading the Severity of Adult and Pediatric Adverse Events, Corrected Version 2.1 – July 2017, will be tabulated by treatment arm for each postvaccination timepoint. Reportable clinical laboratory abnormalities without an associated clinical diagnosis will also be included in the tabulation of AEs described above.

6.3.3.4 Reasons for vaccination discontinuation and early study termination

The number and percentage of participants who discontinue vaccination and who terminate the study early will be tabulated by reason and treatment arm.

6.3.4 Immunogenicity analyses

6.3.4.1 General approach

For the statistical analysis of immunogenicity endpoints, data from enrolled participants will be used according to the initial randomization assignment regardless of how many injections they received. Additional analyses may be performed, limited to participants who received all scheduled injections per protocol. Assay results that are unreliable are excluded; results from specimens collected outside of the visit window, or from HIV-infected participants post-infection, may be excluded. Since the exact date of HIV infection is unknown, any assay data from blood draws 4 weeks prior to an infected participant's last seronegative sample and thereafter may be excluded. If an HIV-infected participant does not have a seronegative sample postenrollment, then all data from that participant may be excluded from the analysis.

Discrete categorical assay endpoints (eg, response rates) will be analyzed by tabulating the frequency of positive response for each assay by antigen and treatment arm at each timepoint for which an assessment is performed. Crude response rates will be presented with their corresponding 95% confidence interval estimates calculated using the score test method (40). Barnard or Fisher's exact tests, as specified in the SAP, will be used to compare the response rates of any 2 vaccine arms, with a significant difference declared if the 2-sided p-value is ≤ 0.05 . In general Barnard's is preferred since under most circumstances it is more powerful than Fisher's exact test (41).

For quantitative assay data (eg, percentage of positive cells from ICS assay), graphical and tabular summaries of the distributions by antigen, treatment arm, and timepoint will be made. For all primary and secondary immunogenicity endpoints, box plots and plots of estimated reverse cumulative distribution curves will be used for graphical display of all of the study arms. Typically, the results will be shown for each vaccine arm.

The difference between arms at a specific timepoint will be tested with a nonparametric Wilcoxon rank sum test if the data are not normally distributed and with a 2-sample t-test if the data appear to be normally distributed. The primary

analysis consists of 4 individual tests comparing the membrane-bound vaccine regimen (BG505 MD39.3 gp151 mRNA) to the membrane-bound knockout (BG505 MD39.3 gp151 CD4KO mRNA) and to the soluble trimer (BG505 MD39.3 mRNA) vaccine arms within each dose level, unless prespecified. That is, we compare Groups 2 vs 1, Groups 2 vs 3, Groups 5 vs 4, and Groups 5 vs 6. Secondary analyses will compare responses between dose levels for each regimen. If no differences are seen between dose levels for a given vaccine regimen, subsequent comparisons of that vaccine regimen may be based on the aggregated arms (eg, pooling over dose). If rank-based tests are used, then the tests will be inverted to construct Hodges-Lehmann point estimates and 2-sided $(1-0.05/15) \times 100\%$ CIs about the differences in location centers of the 3-15 pair-wise comparisons of vaccine arms. If actual-value tests are used then the Dunnett's procedure will be used to construct simultaneous confidence intervals about the pairs of mean differences for the many-to-one comparisons (42) when multiple vaccine arms are each compared with one common control arm. When all pair-wise comparisons between the multiple vaccine arms are of interest, the Tukey procedure (43) will be used. If only specific comparisons between pairs of the multiple vaccine arms are of interest, the Holm-Bonferroni procedure will be used. An appropriate data transformation (eg, \log_{10} transformation) may be applied to better satisfy assumptions of symmetry and homoscedasticity (constant variance). Significance of the differences between pairs will be evaluated using two procedures, first based on whether the simultaneous 95% CIs exclude zero and secondly based on whether the nominal (unadjusted) 95% CIs exclude zero.

Some immunologic assays have underlying continuous or count-type readout that are dichotomized into responder/nonresponder categories (eg, BAMA, TZM-BL). If treatment arm differences for these assays are best summarized by a mixture model, then either Lachenbruch's test statistic (44) or an alternative two-part test (45) (as defined in the SAP) will be used to evaluate the composite null hypothesis of equal response rates in the 2 arms and equal response distributions.

Based upon previous HVTN trials, missing 15% of immunogenicity results for a specific assay is common due to study participants terminating from the study early, problems in shipping specimens, or low cell viability of processed peripheral blood mononuclear cells (PBMCs). To achieve unbiased statistical estimation and inferences with standard methods applied in a complete-case manner (only including participants with observed data in the analysis), missing data need to be missing completely at random (MCAR). Following the most commonly used definition, MCAR assumes that the probability of an observation being missing does not depend on any participant characteristics (observed or unobserved data [ie, the observed data are just a random sample of all the potential data]). When missing data are minimal (specifically if no more than 20% of participants are missing any values), then standard complete-case methods will be used, because violations of the MCAR assumption will have little impact on the estimates and hypothesis tests.

If a substantial amount of immunogenicity data are missing for an endpoint (at least 1 value missing from more than 20% of participants), then using the methods that require the MCAR assumption may give misleading results. In this situation, analyses of the immunogenicity endpoints at a specific timepoint will be performed with methods such as targeted minimum loss-based estimation (TMLE), parametric generalized linear models fit by maximum likelihood, augmented inverse probability weighting (AIPW) methods or multiple imputation methods. TMLE and AIPW are typically preferred because they are doubly robust, providing consistent estimation and appropriate inferences if either the outcome regression or the probability of observing the response value are modeled correctly, under the assumption that the missing data are missing at random (MAR). MAR assumes that the probability of an observation being missing only depends upon the observed responses and upon observed covariates, but not upon any unobserved data. TMLE methods will typically be implemented with the drtmle R package (46) available at CRAN, and will entail specification of a library of learners for the outcome regression and for the probability of observing the response value. When data are not missing at random, sensitivity analyses may be performed as an exploratory analysis. For assessing repeated immunogenicity measurement, linear mixed effects models will be used. If the immunological outcomes are left- and/or right- censored, then the linear mixed effects models of Hughes (47) will be used, because they accommodate the censoring. In addition, secondary analyses of repeated immunogenicity measurements may be done using weighted GEE (48) methods, which are valid under MAR. All of the models described above in this paragraph will include as covariates all available baseline predictors of the missing outcomes.

Some “resource-intensive” immunogenicity endpoints are only measured in subset of participants, eg, fine needle lymph node aspirates and leukapheresis will be performed only on participants consenting to these optional procedures, and immunogenicity endpoints based on these samples will only exist for those participants. For such endpoints, exploratory analyses will be conducted to assess the correlation of participant characteristics measured in (nearly) all participants with the resource-intensive endpoints. For example, if the same assay is performed on blood and fine needle lymph node aspirate samples, then a scatterplot and Spearman rank correlation coefficient (r) will be used to assess the correlation of responses. If at least moderate correlations exist (eg, $r \geq 0.3$), then TMLE is the preferred method estimate the mean of the resource-intensive endpoint for each group and to compare means between groups. Another potential method to apply is the semiparametric locally efficient analysis method of Rotnitzky and Robins (49) as described in Gilbert, Sato et al. for application to vaccine studies (50).

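### Rank-based adjusted intervals for the four primary neutralization contrasts use a divisor of 15 where four would suffice, and neither listed significance rule is named as deciding

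*Protocol*

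**What the plan says.** Protocol section 6.3.4.1 says that the primary "analysis consists of 4 individual tests comparing the membrane-bound vaccine regimen" with the CD4 knockout and with the soluble trimer at each dose level: Groups 2 vs 1, 2 vs 3, 5 vs 4 and 5 vs 6. Dose is a separate question: "Secondary analyses will compare responses between dose levels for each regimen". Arms may be pooled over dose if no dose difference is seen.

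Two branches follow.

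- **Rank tests.** Hodges-Lehmann estimates are given with two-sided intervals at level 1 − 0.05/15, described as "CIs about the differences in location centers of the 3-15 pair-wise comparisons of vaccine arms".
- **Actual-value tests.** Dunnett is used for several arms against a common comparator and Tukey for all pairs. Then: "If only specific comparisons between pairs of the multiple vaccine arms are of interest, the Holm-Bonferroni procedure will be used".

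The paragraph closes with two significance rules. The adjusted one comes first: "Significance of the differences between pairs will be evaluated using two procedures, first based on whether the simultaneous 95% CIs exclude zero". The other makes the same check on intervals without adjustment. The text does not say which rule decides or what is concluded when they differ.

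Response rates are outside this point. They have a single rule, "with a significant difference declared if the 2-sided p-value is" at most 0.05. The two-part test is also outside it; that test applies "If treatment arm differences for these assays are best summarized by a mixture model".

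Section 6.3 waives adjustment across multiple primary immunogenicity endpoints. Section 6.1.1 and Table 6-3 give power at two-sided 0.05 or one-sided 0.025. SAP section 2 limits the supplied SAP to safety.

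**The concern.** A fixed divisor of 15 fits one family only, all pairs of six arms. The same sentence allows for as few as three comparisons, and the primary family has four. An interval meant to hold at 95% across four contrasts is therefore set much wider than it needs to be.

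In the t-test branch the same contrasts get procedures that scale to the number of comparisons. How strict the adjusted analysis is then depends on whether the titres look normal.

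These contrasts are primary objective 2 (section 3.1). If the adjusted intervals carry the conclusion, the excess width costs real sensitivity. If the nominal intervals carry it, the family error should be stated. The plan does not say which applies, and a reader of section 6.1.1 cannot tell which rule the power figures serve.

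**Working it through.** **Inputs.** Four contrasts and divisor 15 (section 6.3.4.1); 15 evaluable per arm, SD 0.85 for log10 ID50, two-sided 0.05 (section 6.1.1); one-sided 0.025 Wilcoxon (Table 6-3). Assumption: normal log10 titres with equal SD.

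**1. Reproduce the stated power.** For 11-fold, the standardized difference is log10(11)/0.85 = 1.041/0.85 = 1.225 SD. The noncentrality is 1.225 × √(15/2) = 3.36 on 28 df. Power at two-sided 0.05 is 89.9%; the plan states 90%. For the Wilcoxon test at 1.1 SD, simulation against the exact null gives 79.8%; the plan states 80%. Every row of Table 6-3 agrees within 2 points. The figures are right at the level they declare.

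**2. Where 15 comes from.** Six arms give 6 × 5/2 = 15 pairs. The rank intervals are at 1 − 0.05/15 = 99.67%. For four contrasts, Bonferroni needs 1 − 0.05/4 = 98.75%.

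**3. Family error over the four contrasts at 0.05/15.** The bound is 4 × 0.05/15 = 1.33%. Simulating null trials with the comparator arm shared within each dose gives about 1.2% with exact rank tests and 1.3% with normal statistics. Over all 15 pairs, the family the divisor fits, it is 3.9%.

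**4. Width.** The ratio of normal quantiles, 0.05/15 to 0.05/4, is 1.18. Simulated mean Hodges-Lehmann widths at n = 15 are 1.56 SD (nominal), 2.01 SD (0.05/4) and 2.39 SD (0.05/15). So 2.39/2.01 = 1.19, in line with the quantile ratio.

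**5. Power and error by level, n = 15 per arm.**

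| Level | Family error over four (rank) | Wilcoxon power at 1.1 SD | t-test power at 11-fold | Fold difference with 90% power (t-test) |
|---|---|---|---|---|
| 0.05 | 16% | 80% | 90% | 11.0 |
| 0.05/2 | about 8% | 71% | 83% | 14.0 |
| 0.05/4 | 4.2% | 60% | 75% | 17.5 |
| 0.05/15 | 1.2% | 41% | not used in this branch | not used in this branch |

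With normal statistics the nominal family error is 17%.

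**6. Separate the two effects.** At 1.1 SD the full drop is 80% − 41% = 39 points. Adjusting for four contrasts accounts for 80% − 60% = 20 points. The remaining 60% − 41% = 19 points comes from using 15 instead of four.

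**7. The t-test branch.** At 11-fold, Dunnett within a dose gives 85%. Holm over four gives 75% if one effect is present and 86% if all four are.

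**8. Undetectable titres.** Assume 30–70% of the comparator arm is at the detection floor and use an exact test with ties. Power at 1.1 SD is then 59–52% at 0.05/4 and 40–33% at 0.05/15, a similar gap. The floor share is an assumption; the documents give no human figure.

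**The case against.** The best defence has several parts.

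- **A divisor of 15 is conservative, not invalid.** This stands. It controls error for every smaller family. A reader might infer that the plan inflates false positives through this divisor; it does the opposite.
- **The text does not call the 0.05/15 intervals simultaneous.** Also true. They are, however, the only adjusted intervals written for rank tests, so the first significance rule has nothing else to refer to in that branch.
- **Holm may cover both branches.** The Holm sentence does not mention actual-value tests, Holm works on p-values from any test, and the four contrasts are specific comparisons. That reading is possible. But the sentence follows the actual-value procedures, the closing rule is worded in intervals, and nothing withdraws the written 0.05/15.
- **Section 6.3 waives adjustment.** It does so across endpoints. It does not address contrasts within one endpoint, and section 6.3.4.1 lists the adjusted rule first.
- **Reporting both intervals is open and suits a phase 1 trial.** Section 2.3 says the products are not on a path to licensure. This carries weight: the missing deciding rule is mainly a wording gap.
- **An immunogenicity SAP may settle it.** Section 6.3.4.2 defers assay detail to an SAP, and the supplied one covers safety only. Such a document could name the rule and the family; on the text available, neither is fixed.

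Two stronger readings are tempting. One is that the stated power is wrong. It is not: the level is disclosed and the figures reproduce. The other is that the divisor halves the 80% power. It does not: about half of that loss is the price of any adjustment for four contrasts.

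**Conclusion.** The point holds for neutralization magnitude when rank tests are used. The adjusted intervals are valid but too wide for the four primary contrasts: family error is about 1.2% against an intended 5%, width is about 18% more than at 0.05/4, and Wilcoxon power at 1.1 SD is about 41% against 60%. The adjusted standard also differs between the rank and t-test branches without a stated reason.

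The undeclared deciding rule is a smaller, linked gap. The power in section 6.1.1 is correct for the nominal rule only, and that rule carries about 16–17% family error over the four contrasts.

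The result rests on reading the 0.05/15 intervals as the simultaneous ones, on 15 evaluable per arm, and on normal log10 titres with equal SD.

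**What to change.** In section 6.3.4.1:

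- Replace 0.05/15 with 0.05/4 for the four primary contrasts. For any other family, such as the between-dose or pooled comparisons, use the number of comparisons actually made.
- Use the same family in both branches. Holm over four in the t-test branch would match 0.05/4.
- If each dose level is preferred as its own family, use 0.05/2 with Dunnett within dose, and state that error over all four contrasts is then about 8% in the rank branch.
- Name the rule that decides and label the other intervals supportive.

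In section 6.1.1, say that the power applies to the nominal rule. If that rule decides, keep the figures, state the 16–17% family error, and still correct the divisor of the supportive intervals. If the adjusted rule decides at 0.05/4 with 15 per arm, 90% power needs about a 17.5-fold difference instead of 11-fold. The n = 15 column of Table 6-3, for 0.8 to 1.3 SD, becomes about 30, 40, 49, 60, 69 and 77%.

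The cost is wording, plus a rerun power table and less favourable stated power if the adjusted rule decides. Sample size does not change.

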2.2.2.2 In non human primates (NHPs)

Five groups of six rhesus macaques were immunized via IM injection bilaterally in each deltoid at weeks 0, 8 and 24 using BG505 MD39.3 constructs listed below.

1. BG505 MD39.3 soluble trimer delivered by mRNA (100 mcg total dose)
2. BG505 MD39.3 gp151 membrane-bound trimer delivered by mRNA (100 mcg total dose)
3. BG505 MD39.3 CD4KO gp151 membrane-bound trimer delivered by mRNA (100 mcg total dose)
4. BG505 MD39.3 gp151 membrane-bound trimer delivered by mRNA (300 mcg total dose)
5. BG505 MD39.3 soluble trimer delivered with adjuvant (100 mcg protein + 750 mcg SMNP adjuvant total dose)

All five groups elicited similar levels of binding antibodies at assessed at weeks 10 and 26 with the binding titers increasing for all groups following the third immunization at week 24 (Figure 2-5).

[figure not shown]

Figure 2-5 ELISA analysis of serum antibody binding responses from week 10 (post two immunizations) and week 26 (post three immunizations) in NHPs

None of the animals receiving BG505 MD39.3 soluble trimer delivered by mRNA developed autologous neutralizing antibodies even after three immunizations (Figure 2-6, Grp1). Half of the animals receiving the 100 mcg dose of BG505 MD39.3 gp151 membrane-bound trimer delivered by mRNA developed detectable autologous neutralizing antibodies at week 10 which increased in potency at week 26 (Figure 2-6, Grp2). Two of six animals receiving the 100 mcg dose of BG505 MD39.3 gp151 CD4KO membrane-bound trimer delivered by mRNA developed autologous neutralizing antibodies at week 26 (Figure 2-6, Grp3). Four out of the six animals in the group receiving the 300 mcg dose of BG505 MD39.3 gp151 membrane-bound trimer delivered by mRNA developed detectable autologous neutralizing antibodies at week 26 (Figure 2-6, Grp4). A similar response was seen in the BG505 MD39.3 soluble trimer delivered with adjuvant group (Figure 2-6, Grp5). Overall, BG505 MD39.3 gp151 membrane-bound trimers delivered by mRNA elicited similar antibody responses compare to soluble trimer protein + adjuvant.

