6.1.1 Power calculations for immunogenicity

The immunogenicity sample size calculations allow for a 15% rate of missing immunogenicity data at Month 6.5. Of the n=18 enrolled per arm, we assume n=15 will be available for analysis.

A primary objective is to evaluate the ability of the BG505 MD39.3 trimer mRNA vaccines to elicit autologous neutralizing antibodies. The primary endpoint will be the occurrence and magnitude of serum antibody neutralization of pseudoviruses (BG505 T332N) as measured by the TZM-bl assay two weeks after the third vaccination which will be compared between the membrane-bound vaccine regimen (BG505 MD39.3 gp151 mRNA) and the membrane-bound knockout (BG505 MD39.3 gp151 CD4KO mRNA) and between the membrane-bound vaccine regimen (BG505 MD39.3 gp151 mRNA) and the soluble trimer (BG505 MD39.3 mRNA) vaccine arms, within each dose level. Secondary analyses will test for differences between dose levels. If no significant difference is seen between the 100mcg and 250mcg dose (eg, between Groups 1 and 4, between Groups 2 and 5 or between Groups 3 and 6), secondary analyses may aggregate over dose groups for comparisons between the vaccine regimens. For example, if no significant difference is seen between doses for the soluble trimer regimen in Groups 1 and 4 or between doses for the membrane-bound vaccine regimen in Groups 2 and 5, we may aggregate over the dose to compare responses of Groups 1 and 4 (n=30) to Groups 2 and 5 (n=30).

The precision with which the true immune response rate can be estimated from the observed data depends on the true underlying response rate and the sample size. Two-sided 95% confidence intervals for the response rate based on observing a particular rate of responses in the vaccinees is shown in [Table 6-1](#). Calculations are done using the score test method (29).

Table 6-1 Two-sided 95% confidence intervals for the true response rate based on observing a particular rate of responses in the vaccinees (n = 15, 30)

No. of responses	Observed response rate (%)	95% Confidence interval
4/15	26.7	(9.0, 51.9)
7/15	46.7	(24.8, 69.9)
11/15	73.3	(48.0, 89.1)
12/15	80.0	(54.8, 93.0)
8/30	26.7	(14.2, 44.4)
15/30	50.0	(33.2, 66.8)
22/30	73.3	(55.6, 85.8)
24/30	80.0	(62.7, 90.5)

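### For neutralization titres heaped at the assay floor, the rule that the Hodges-Lehmann interval must exclude zero can contradict the rank-sum test it inverts, and the plan does not say which governs

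*Protocol*

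**What the plan says.** Primary endpoint 2 (Protocol 3.1) covers occurrence, magnitude and response rate of TZM-bl neutralization two weeks after the third vaccination. Protocol 6.3.4.1 has four provisions that bear on it:

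- **Response rate.** Barnard or Fisher tests "will be used to compare the response rates of any 2 vaccine arms", with significance at two-sided p ≤ 0.05.
- **Magnitude.** Arms are "tested with a nonparametric Wilcoxon rank sum test if the data are not normally distributed" and otherwise with a t-test. The primary contrasts are: "we compare Groups 2 vs 1, Groups 2 vs 3, Groups 5 vs 4, and Groups 5 vs 6". No p-value threshold is attached to the rank-sum test.
- **Intervals and significance.** If rank tests are used, "the tests will be inverted to construct Hodges-Lehmann point estimates" and intervals at level 1 − 0.05/15. Significance of pairwise differences is then judged "first based on whether the simultaneous 95% CIs exclude zero and secondly based on whether the nominal (unadjusted) 95% CIs exclude zero".
- **Two-part test.** For assays dichotomized into responder and non-responder, TZM-bl being one of the examples, a Lachenbruch or other two-part test is used if a mixture model is the best summary. No criterion is given, and the choice of test is left to the SAP.

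The SAP supplied is limited to safety data (SAP section 2) and defines no two-part test.

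**The concern.** The Hodges-Lehmann interval estimates a pure shift between two continuous distributions. Non-responders in a neutralization assay share one floor value, so many between-arm differences are exactly zero. These zeros can hold the interval limit at zero however high the responders' titres are.

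The protocol's own animal data make this plausible. On the soluble trimer, section 2.2.2.2 reports: "None of the animals receiving BG505 MD39.3 soluble trimer delivered by mRNA developed autologous neutralizing antibodies even after three immunizations". With the membrane-bound products, 3 of 6 animals had neutralization on gp151 at 100 mcg, 4 of 6 on gp151 at 300 mcg, and 2 of 6 on CD4KO.

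At stake is the magnitude verdict in the four primary contrasts. A real gp151 advantage could be reported as non-significant in magnitude beside a significant response-rate result from the same samples, with no rule to reconcile them.

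**Working it through.** **Inputs.** From Protocol 6.1.1: "Of the n=18 enrolled per arm, we assume n=15 will be available for analysis"; SD of log10 ID50 0.85. From 6.3.4.1: interval levels 95% and 1 − 0.05/15 = 99.67%. Assumptions not in the documents: human response rates, the responders' titre distribution, and one common value for all non-responders.

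**1. The plan's own power figures.** An 11-fold difference is log10(11) = 1.041. With SD 0.85, n = 15 per arm and a two-sided t-test at 0.05, power is 89.9% (plan: 90%). Simulating the Wilcoxon test on untied normal data at 1.1 SD gives 80.0% (Table 6-3: 80%). Both reproduce, but neither calculation has a floor or uses the interval rule.

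**2. Which ordered difference is the lower limit.** There are 15 × 15 = 225 differences. From the exact null distribution of U:
- 95%: P(U ≤ 64) = 0.0227, within 0.025, and P(U ≤ 65) = 0.0251, above it. The lower limit is the 65th smallest difference.
- 99.67%: P(U ≤ 43) = 0.00158, within 0.05/30 = 0.00167, and P(U ≤ 44) = 0.00184, above it. The lower limit is the 44th smallest.

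**3. Tie count.** With 0/15 responders in one arm and r/15 in the other, 15 × (15 − r) differences are exactly zero. The lower limit exceeds zero only if this count is at most 64 (r ≥ 11) or at most 43 (r ≥ 13).

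| r/15 v 0/15 | Zero differences | Rank-sum p (tie-corrected normal) | Fisher p | 95% interval excludes 0 | 99.67% interval excludes 0 |
|---|---|---|---|---|---|
| 4 | 165 | 0.038 | 0.100 | no | no |
| 5 | 150 | 0.018 | 0.042 | no | no |
| 8 | 105 | 0.0015 | 0.0022 | no | no |
| 10 | 75 | 0.0002 | 0.0002 | no | no |
| 11 | 60 | 0.00008 | 0.00005 | yes | no |
| 12 | 45 | 0.00003 | 0.00001 | yes | no |
| 13 | 30 | 0.000009 | 0.000002 | yes | yes |

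The rank-sum column is the normal approximation. When one arm is wholly at the floor, the exact permutation p is 2 × C(15,r)/C(30,r), the same as Fisher. At r = 4 it is 2 × 1365/27405 = 0.0996; at r = 5, 2 × 3003/142506 = 0.042. The exact version therefore reaches significance from 5/15 rather than 4/15, still far below 11/15.

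**4. Software.** R's wilcox.test returns a 95% lower limit of 0.0000 at 8/15 v 0/15, 0.00007 at 10/15 and 1.0 at 11/15. At 99.67% it returns 0.00005 at 11/15 and 1.0 at 12/15. Limits of 0.00007 or 0.00005 reflect root-finder tolerance, not evidence.

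**5. Power at n = 15 per arm.** Responders' log10 titres have mean 1 above the floor and SD 0.85, truncated above the floor. Interval and rank-sum columns are from 4,000 simulated trials per scenario; Fisher is by exact enumeration.

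| True response | 95% interval rule | Rank-sum p ≤ 0.05 | Fisher on response rate |
|---|---|---|---|
| 50% v 0% | 6% | 98% | 94% |
| 70% v 10% | 36% | 94% | 89% |
| 80% v 20% | 54% | 89% | 87% |

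Barnard's test gives about 94% or more in all three rows. Other responder titres (log10 mean 2, SD 0.4) again give 6% v 98% at 50% v 0%. With equal 40% response in both arms, the 95% interval rule rejects about 0.1% of the time and the rank-sum test about 4.4%.

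**6. Dependence on the number of floor values.** For the design's 11-fold shift (SD 0.85) with values below a floor censored:

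| Control arm detectable | 95% interval rule | Rank-sum p ≤ 0.05 |
|---|---|---|
| 100% | 87% | 87% |
| 50% | 74% | 86% |
| 33% | 51% | 84% |
| 20% | 20% | 78% |
| 10% | 2% | 67% |

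**The case against.** A reader might infer that the interval rule is the sole decision rule for neutralization, and that a large gp151 advantage would be missed on primary endpoint 2. The documents do not support that. Section 6.3.4.1 specifies the Wilcoxon test itself and describes the primary analysis as four tests. It also compares response rates, part of the same endpoint, at p ≤ 0.05. At 8/15 v 0/15 Fisher gives 0.002, so the difference would be declared there.

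The next paragraph of the protocol also anticipates the problem by offering a two-part test and naming TZM-bl. A separate immunogenicity SAP, not supplied, may define it.

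Two technical objections have force. Strictly inverting the tie-corrected test rejects zero exactly when its p-value is below 0.05, so the conflict comes from using untied order statistics or from reporting an open limit as 0. The 13/15 threshold also depends on implementation, since R gives about 12. Finally, the animal groups had six animals each, and section 2.2.2.2 itself warns that animal models do not reliably predict human responses.

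These points narrow the finding but do not remove it. The interval rule is the only significance criterion written for magnitude on this branch, the two-part provision has no trigger, and nothing says which result stands when they disagree.

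**Conclusion.** The point holds for the magnitude component of primary endpoint 2, on the rank-based branch, when many titres sit at the floor. There the written rule can give a falsely non-significant magnitude result that conflicts with the rank-sum test and with the response-rate result. Against an arm with no responders, the order-statistic interval needs 11/15 or 13/15 responders, whereas the rank-sum p needs 4/15 (5/15 by exact permutation). Near the interval thresholds the verdict can turn on tie handling and numerical tolerance.

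The tie counts need only a common floor value and 15 evaluable per arm. The power figures also rest on the assumed response rates and titres. With few floor values the rules agree. This should be fixed, but it does not put detection of a response-rate difference at risk.

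**What to change.** In Protocol 6.3.4.1, and in the immunogenicity SAP if there is one, add for assays with a floor:

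1. Judge the magnitude contrasts 2 v 1, 2 v 3, 5 v 4 and 5 v 6 on the tie-corrected rank-sum p-value, preferably by permutation, at the applicable alpha. Alternatively, use the plan's own two-part test with a fixed trigger, such as a stated proportion of values at the floor. Name the version of the test, since the normal and permutation p-values differ at 4/15 v 0/15.
2. State that this result governs over the interval rule.
3. Keep the Hodges-Lehmann estimate and interval as descriptive. The probability that a participant in one arm has a higher titre than one in the other, ties counted half, is an optional effect size.

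The cost is about one paragraph of text and no new data. The choice should be fixed before the primary neutralization results are analysed.
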